- Ask the subjects to verbally report if any medications have been started or stopped since last visit.
- Urine pregnancy test for women of child-bearing potential
- Collect oral wash sample
 - Provide subject with a cup with 10mL of mouthwash
 - Ask subject to swish vigorously for at least 30 seconds then spit back into the same cup (no brushing for 120 minutes and eating for 10 minutes before collection)
 - Ask the subject to complete the oral wash antibiotic usage questionnaire
- Perform a physical examination per standard of care
- Take vital signs
- Blood will be drawn for
 - Immunomonitoring and other analyses (eight 10.0 mL rubber green top sodium heparin tubes)
 - CBC with diff
 - Chem 7 and LFTs
- Distribute stool collection kit to subject with instructions, including the stool sample antibiotic usage questionnaire to be completed on the days of stool collection.

VISIT 9 (6 MONTHS AFTER VISIT #8 ± 30 DAYS)

- Ask the subjects to verbally report if they have experienced any side effects since the last injection.
- Ask the subjects to verbally report if any medications have been started or stopped since last visit.
- Ask the subject to complete the Visit 9 Questionnaire
- Urine pregnancy test for women of child-bearing potential
- Perform a physical examination per standard of care
- Take vital signs
- Blood will be drawn for
 - Immunomonitoring and other analyses (eight 10.0 mL rubber green top sodium heparin tubes)
 - CBC with diff
 - Chem 7 and LFTs

Optional Follow Up Visit

A follow-up visit may be scheduled after the screening visit, after the vaccination visits, and at any
time during study participation to receive follow-up instructions, be evaluated for AEs, or address
study-related concerns as needed.

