7.2 SAFETY ASSESSMENTS

As one of the primary endpoints of this study is safety, the monitoring of AEs will be diligently recorded and reviewed. In the clinical setting, subjects will report any AEs since their last visit and immediately following each vaccination. Additionally, vital signs will be taken pre- and post-vaccination to monitor for

fluctuations in these parameters. Vital signs will be taken and blood drawn (CBC with diff, Chem 7, and LFTs) regularly throughout the study.

ASSESSMENT OF ADVERSE EVENTS

A physician, or designee, will evaluate a subject's AEs based on the NCI CTCAE Version 5.0. A physician will assess whether or not a particular event is likely to be related to the study drug. For more details on event reporting, see Section 7.4.

MONITORING TOXICITY

Injection-induced/related serious toxicity will be defined (using CTCAE Version 5.0) as:

- Grade II or higher allergic reactions. Grade II is defined as "Oral intervention indicated". Grade III is defined as "Bronchospasm; hospitalization indicated for clinical sequelae; intravenous intervention indicated".
- Grade II or higher autoimmune reactions/disorders. Grade II is defined as "evidence of autoimmune reaction involving a non-essential organ or function (e.g., hypothyroidism)". Grade III is defined as "autoimmune reactions involving major organ (e.g., colitis, anemia, myocarditis, kidney)".
- Any Grade III or higher event.

Subjects who have any of the above dose-limiting toxicities will be treated and referred for additional care as indicated with systemic steroids, topical steroids, epinephrine or Benadryl. These subjects will no longer receive the vaccine but will continue with assessments per the study calendar, including collection of study labs.

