7.4 ADVERSE EVENTS AND SERIOUS ADVERSE EVENTS

DEFINITION OF ADVERSE EVENTS (AES)

Adverse event means any untoward medical occurrence associated with the use of an intervention in humans, whether or not considered intervention-related (21 CFR 312.32 (a)).

DEFINITION OF SERIOUS ADVERSE EVENTS (SAES)

An AE or suspected adverse reaction is considered "serious" if, in the view of either the investigator or sponsor, it results in any of the following outcomes: death, a life-threatening AE, inpatient hospitalization or prolongation of existing hospitalization, a persistent or significant incapacity or substantial disruption

of the ability to conduct normal life functions, or a congenital anomaly/birth defect. Important medical events that may not result in death, be life-threatening, or require hospitalization may be considered serious when, based upon appropriate medical judgment, they may jeopardize the subject and may require medical or surgical intervention to prevent one of the outcomes listed in this definition.

To avoid confusion, as the terms "serious" and "severe" are not synonymous, the following clarification is given: The term "severe" is often used to describe the intensity (severity) of a specific event (as in mild, moderate or severe myocardial infarction); the event itself, however, may be of relatively minor medical significance (such as severe headache). This is *not* the same as "serious," which is based on subject/event *outcome* or *action* usually associated with events that pose a threat to a subject's life or functioning. Seriousness (not severity) serves as a guide for defining regulatory reporting obligations. [ICH-E2A(II)(B)]

CLASSIFICATION OF AN ADVERSE EVENT

SEVERITY OF EVENT

AEs will be graded using the NCI CTCAE Version 5.0. A copy of the NCI CTCAE Version 5.0 can be downloaded from the Cancer Therapy Evaluation Program (CTEP) home page. All appropriate treatment areas have access to a copy of the NCI CTCAE Version 5.0.

RELATIONSHIP TO STUDY INTERVENTION

All AEs must have their relationship to study intervention assessed by the clinician who examines and evaluates the subject based on temporal relationship and his/her clinical judgment. The degree of certainty about causality will be graded using the categories below. In a clinical trial, the study product must always be suspect.

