The local site PI or a local site Sub Investigator will be responsible for determining whether an AE is expected or unexpected. Vaccine-related or possibly vaccine-related AEs, which occurred with ≥5% of injections, in the order of decreasing number of occurrences, were injection-site reaction (immediate and delayed), myalgia, headache, nausea, fatigue, hypokalemia, fever, and flu-like symptoms [36, 37]. None of these AEs was more than grade 2. An AE will be considered unexpected if the nature, severity, or frequency of the event is not consistent with the risk information previously described for the study intervention.

TIME PERIOD AND FREQUENCY FOR EVENT ASSESSMENT AND FOLLOW-UP

The occurrence of an AE or SAE may come to the attention of study personnel during study visits and interviews of a study subject presenting for medical care, or upon review by a study monitor.

All AEs occurring during the study period must be recorded. The clinical course of each event should be followed until resolution, stabilization, or until it has been determined that the study treatment or participation is not the cause. SAEs that are still ongoing at the end of the study period must be followed for up to 30 days to determine the final outcome. Any SAE that occurs after the study period and is considered to be possibly related to the study treatment or study participation should be recorded and reported immediately to the Sponsor.

Multi-sites will capture adverse event source documentation within their electronic medical record system. Information to be collected may include event description, time of onset, clinician's assessment of severity, relationship to study product (assessed only by those with the training and authority to make a diagnosis), and time of resolution/stabilization of the event. All AEs occurring while on study must be documented appropriately regardless of relationship. All AEs will be followed to adequate resolution or to study termination. Additionally, the main site will document AEs in AR-AERS and the external sites will document AEs on a provided AE Log to ensure that all information is captured uniformly across multi-sites. All AEs including local and systemic reactions not meeting the criteria for SAEs will be captured on the appropriate electronic Case Report Form (eCRF) in OpenClinica (OC).

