Any medical condition that is present at the time that the subject is screened will be considered as baseline and not reported as an AE. However, if the study subject's condition deteriorates or exacerbates at any time during the study, it will be recorded as an AE.

Changes in the severity of an AE will be documented to allow an assessment of the duration of the event at each level of severity to be performed. AEs characterized as intermittent require documentation of onset and duration of each episode.

Study staff responsible for reporting AEs will be listed on the Delegation Log and will record all reportable events with start dates occurring any time after informed consent has been obtained until the end of study participation. At each study visit, the investigator, or a designee, will inquire about the occurrence of

AEs/SAEs since the last visit. Events will be followed for outcome information until resolution or stabilization.

A summary of AEs will be included in the annual IRB status report and the IND report to the FDA.

SERIOUS ADVERSE EVENT REPORTING

A serious, unexpected (previously not expected in nature, severity, or degree of incidence), and drug-related AE must be reported to:

- ORRA and UAMS PI within 24 hours of local site PI being notified.
- The FDA will be notified using the MedWatch Form FDA 3500A within 10 days of local site PI being notified. The local site PI will report to ORRA and UAMS PI; ORRA will report to FDA.
- The UAMS IRB will be notified of events requiring expedited reporting within 10 days of local site PI being notified (see below if SAE is death).
- A drug-related death or event that is considered life-threatening occurring while a subject is on the study must be reported to the UAMS IRB immediately and to the FDA within 7 days of the investigator learning of the event.
- THE CAUSE OF DEATH AND THE INVESTIGATOR'S DISCUSSION REGARDING WHETHER OR NOT THE DEATH WAS DRUG-RELATED SHOULD BE DESCRIBED IN A WRITTEN REPORT.

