8.2 STATISTICAL ANALYSES

Subjects who received at least one dose of the vaccine will be included in safety assessments. Safety analyses will include summaries of the incidence of AEs using the NCI CTCAE Version 5.0 that occur during the study period regardless of causality. The AEs will be mostly descriptive initially. However, after unblinding at the completion of the study, rates of common side effects (occurring with 5% or more injections) will be compared between the PepCan and the placebo arms. Efficacy will be assessed by comparing cancer recurrence rate between the 2 arms. The expected number of head and neck cancer patients who achieve remission is 100 patients per year. For immunological assessments, the presence of new anti-HPV-16 E6 T-cell activity will be measured using CD3 ELISPOT assay, and its statistical significance will be assessed using a paired *t*-test. For analyses of immune cells such as Th1, Th2, Treg, and MDSCs, percentages before and after vaccination will also be assed using a two-tailed paired *t*-test. The frequencies between subjects who experience recurrence and those that do not in the PepCan arm will be compared using Wilcoxon rank-sum test. The diversity of gut microbiome will be assessed prior to

injection, and will be compared to that after injection using alpha diversity, beta diversity, and compositions at the phylum or family levels. These parameters will also be compared between subjects with and without recurrence with in the PepCan arm.

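### The lists for Visits 2 to 9 prompt for side effects dated from the last injection, which conflicts with the all-cause inquiry since the last visit in 7.2 and 7.4 and the all-cause analysis in 8.2

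*Combined protocol and SAP*

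**What the plan says.** The synopsis and section 3 make adverse events over two years the primary outcome. The instructions for collecting and analysing them are these:

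- **7.1, lists for Visits 2 to 9.** Each of the eight lists has the line "Ask the subjects to verbally report if they have experienced any side effects since the last injection". It is the only adverse event history question in those lists. The line after it, on medication changes, is dated from the last visit.
- **7.2.** "In the clinical setting, subjects will report any AEs since their last visit and immediately following each vaccination".
- **7.4, definition.** "Adverse event means any untoward medical occurrence associated with the use of an intervention in humans, whether or not considered intervention-related".
- **7.4, inquiry.** "At each study visit, the investigator, or a designee, will inquire about the occurrence of" AEs and SAEs since the preceding visit.
- **7.4, documentation.** "All AEs occurring while on study must be documented appropriately regardless of relationship". Delegated staff "will record all reportable events with start dates occurring any time after informed consent has been obtained until the end of study participation".
- **8.2.** Safety analyses summarise the incidence of AEs "that occur during the study period regardless of causality".
- **11.1.** The schedule has an Adverse Events row marked at Visits 1 to 9.

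**The concern.** *Side effect* is an attribution; *adverse event* is not. A subject asked about side effects decides what the injection caused before any clinician hears of the event. Yet 7.4 reserves the assessment of relationship for people with the training and authority to make a diagnosis.

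The setting makes this more than a point of style. Under inclusion criterion 3, subjects have finished curative surgery, radiation and/or chemotherapy within the previous 120 days, so many symptoms have another obvious explanation. An event that a subject puts down to earlier treatment may go unmentioned, although the all-cause summary in 8.2 needs it.

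The filter may also work differently in the two arms. Section 2.1 reports injection-site reactions as the most common events with PepCan, and the comparator is saline. Subjects with a visible local reaction may be readier to blame later symptoms on the injection. After unblinding, 8.2 compares rates of common side effects between the arms, so unequal reporting could enter that comparison. Adverse event reports also feed the 10% suspension rule in 9.2.

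**Working it through.** There is no planned figure to reproduce, since the point concerns wording. Two checks apply: what each instruction asks for, and how far back it reaches.

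**Content**

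| Place | What is asked for or used | Attribution needed? | Dated from |
|---|---|---|---|
| 7.1, Visits 2–9 | side effects | yes, by the subject | last injection |
| 7.2 | any AEs | no | last visit, plus just after each injection |
| 7.4 | AEs and SAEs; all documented | no | last visit |
| 8.2 | AE incidence in the study period | no | not applicable |

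The visit lists differ from 7.2 and 7.4 both in the term and in the reference date.

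**Look-back**

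Inputs from 7.1: injections are given at Visits 1 to 7 and none at Visits 8 and 9. The nominal gaps are 3 weeks (Visits 1 to 4), 3 months (Visits 4 to 7) and 6 months (Visits 7 to 9). For a subject who receives every injection on schedule:

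| Visit | Since last injection | Since last visit |
|---|---|---|
| 2, 3, 4 | 3 weeks | 3 weeks |
| 5, 6, 7 | 3 months | 3 months |
| 8 | 6 months | 6 months |
| 9 | 6 + 6 = 12 months | 6 months |

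At Visit 9 the visit-list period covers again the six months already asked about at Visit 8.

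Sections 7.2 and 9.2 keep subjects on assessments after injections are stopped for toxicity, and for them the gap is wider. Take a subject stopped after the first injection. At Visit 9, the time since that injection is 3 × 3 weeks + 3 × 3 months + 2 × 6 months = 9 weeks + 9 months + 12 months, or about 23 months. The time since the last visit is 6 months.

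Injections are given only at scheduled visits, so the last injection can never be more recent than the last scheduled visit. The visit-list period is therefore equal or longer, never shorter. The narrowing lies in the term alone. The date adds a longer and overlapping recall period at Visit 9 and after early stopping.

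**The case against.** The strongest reply is that the operative safety sections already state the right rule. Section 7.4 orders an AE and SAE inquiry at each study visit, 7.2 agrees, and 11.1 schedules adverse events at Visits 1 to 9. A reader might infer from 7.1 that the primary endpoint is collected only through the narrower question. The documents do not support that: they hold two differing instructions for the same visits.

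Other routes also do not depend on what the subject blames. Medication changes are asked about at every visit. Blood counts, chemistry and liver tests are drawn at Visits 1, 3 and 5 to 9, and examinations are done at Visits 5 to 9. Vital signs are taken throughout. Section 7.4 adds contacts for medical care and monitor review. These offset part of the risk, but least for symptoms that leave no laboratory or examination sign and lead to no treatment, where the verbal question matters most.

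The protocol also uses *side effects* loosely. Section 8.2 passes from AEs to common side effects within two sentences, and the 7.1 line instructs staff without being shown to be a verbatim script. That makes an innocent drafting origin likely. It does not tell a site which instruction to follow.

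Finally, the Data Collection and Management Responsibilities text in 9.2 says visit worksheets will be supplied as source documents, and their wording is not in the documents. It is therefore unknown what staff actually ask. This stands, and it is why the point is a risk and not a finding of lost data.

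**Conclusion.** The conflict is real and concerns the primary endpoint. If staff follow the visit lists, all-cause events pass first through the subject's own attribution, which 7.2, 7.4 and 8.2 do not intend. In time, the mismatch is nil at Visits 2 to 8 for a subject on schedule. It is about 12 against 6 months at Visit 9, and up to about 23 against 6 months for a subject stopped after one injection who stays on assessments.

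Three stronger readings are not supported:

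- **That the recall period is too short.** It is never shorter than the period in 7.4.
- **That events have been or will be lost.** This depends on which instruction and worksheet wording the sites use.
- **That a bias of known size arises between the arms.** The documents give no reporting rates by arm, so any percentage would be invented. Unequal reporting is plausible because saline is compared with a product known for local reactions, but no more than that can be said.

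The conclusion assumes that at least some sites work from the 7.1 lists, or from worksheets that copy them. On that footing the passages should be reconciled.

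**What to change.** In the 7.1 lists for Visits 2 to 9, replace the line with: *Ask about any new or worsened health problem since the last visit, whether or not the subject thinks it is related to the injection.* Check the visit worksheets and make the same change if they carry the present wording.

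This brings the visit lists into line with 7.2, 7.4 and 8.2 in both content and reference date. It also removes the overlapping recall at Visit 9 and the long recall for subjects who have stopped injections.

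The cost is a wording amendment and possibly revised worksheets. The downside is somewhat more unrelated events to record, which 7.4 already requires.

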7.2 SAFETY ASSESSMENTS

As one of the primary endpoints of this study is safety, the monitoring of AEs will be diligently recorded and reviewed. In the clinical setting, subjects will report any AEs since their last visit and immediately following each vaccination. Additionally, vital signs will be taken pre- and post-vaccination to monitor for

fluctuations in these parameters. Vital signs will be taken and blood drawn (CBC with diff, Chem 7, and LFTs) regularly throughout the study.

ASSESSMENT OF ADVERSE EVENTS

A physician, or designee, will evaluate a subject's AEs based on the NCI CTCAE Version 5.0. A physician will assess whether or not a particular event is likely to be related to the study drug. For more details on event reporting, see Section 7.4.

MONITORING TOXICITY

Injection-induced/related serious toxicity will be defined (using CTCAE Version 5.0) as:

- Grade II or higher allergic reactions. Grade II is defined as "Oral intervention indicated". Grade III is defined as "Bronchospasm; hospitalization indicated for clinical sequelae; intravenous intervention indicated".
- Grade II or higher autoimmune reactions/disorders. Grade II is defined as "evidence of autoimmune reaction involving a non-essential organ or function (e.g., hypothyroidism)". Grade III is defined as "autoimmune reactions involving major organ (e.g., colitis, anemia, myocarditis, kidney)".
- Any Grade III or higher event.

Subjects who have any of the above dose-limiting toxicities will be treated and referred for additional care as indicated with systemic steroids, topical steroids, epinephrine or Benadryl. These subjects will no longer receive the vaccine but will continue with assessments per the study calendar, including collection of study labs.

7.3 EFFICACY ASSESSMENTS

Studying the efficacy of PepCan and the schedule in which this protocol specifically outlines the clinical response (i.e., reduced cancer recurrence rate) of subjects is a secondary endpoint. Immune response will be evaluated as the tertiary endpoint, and microbial response will be assessed as the quaternary endpoint. This section includes a list and description of the procedures that will be conducted.

ASSESSMENT OF CLINICAL EFFICACY

Cancer recurrence rate will be compared for a 2-year period between the PepCan and placebo arms using Fisher's exact test.

COLLECTION OF BIOLOGICAL SPECIMEN AND URINE SPECIMEN

URINE SPECIMEN

A urine pregnancy test will be administered to subjects of childbearing potential at every visit and the results reviewed by the study team before injection.

ORAL WASH SPECIMEN

- 1. Oral wash specimens will be collected at Screening, Visit 5, Visit 7 and Visit 8.
- 2. Subjects will be asked to swish 10mL of mouthwash and spit into a cup.

BLOOD DRAW

- 1. Blood draw will be performed by a trained phlebotomist or other medical professional
- 2. CBC with differential on Visits Screen, 1, 3, 5, 6, 7, 8, 9
- 3. Chem 7 on Visits Screen, 1, 3, 5, 6, 7, 8, 9
- 4. LFTs on Visits Screen, 1, 3, 5, 6, 7, 8, 9
- 5. 8 rubber green top tubes on Visits 1, 5, 8, 9

STOOL SAMPLE

- 1. Stool samples will be collected with OMNIgene•GUT kit (ref. OMR-200) which includes a toilet accessory sheet, collection tube, and spatula.
- 2. Subjects will be given appropriate packing and shipping supplies to be sent back to UAMS at Visits Screen, 5, 7, and 8 to the following address:

Cancer Clinical Trials Office

[name]

[name]

3. Instructions will be given to the subject at each visit, but the full instructions for the kit can also be found at: http://www.dnagenotek.com/US/support/ciOMR200.html

FUTURE USE OF REMAINING SAMPLES

Subjects may choose to allow future use of remaining samples in the informed consent form. After all tests are completed, any leftover samples will be saved for future research studies on HPV. The blood, cell, oral, and stool samples will be frozen and will be stored with only the subject identifier. The cell samples may be stored indefinitely until needed for a future research study. Subjects who originally chose to allow future use of remaining samples but change their mind later may notify the PI in writing to the address listed in the informed consent form. The subject identifier will be linked to the subject's name and the study team will collect the sample and destroy it per institutional guidelines.

LABORATORY EVALUATIONS

BLOOD SAMPLES

Complete blood count with differential, Chem 7, and liver function tests will be performed at [INSERT LOCAL LAB] in accordance with their current SOPs.

FACS ANALYSIS

Peripheral blood mononuclear cells (PBMCs) isolated from blood samples drawn at Visits 1, 5, 8, and 9 may be analyzed at UAMS to measure circulating immune cells such as Th1, Th2, regulatory T-cell (Treg), and myeloid-derived suppressor cells (MDSCs). HLA typing may be performed using remaining PBMCs.

ELISPOT

An immune assay such as an ELISPOT assay to assess the presence of HPV-specific T-cells will be performed. After each blood draw, PBMCs will be separated into CD14+ and CD14- populations and cryopreserved. To eliminate inter-assay variability, all 4 blood samples (before vaccination, after 4 vaccinations, 7 vaccinations, and at the end of the study) will be used to establish T-cell lines and to

perform ELISPOT assays. CD3 T-cell lines will be established by stimulating in vitro magnetically selected CD3 cells with autologous mature dendritic cells exposed to HPV-16 E6-vac andE6-GST. ELISPOT assays will be performed at UAMS as previously described [36, 37]. We typically examine 10 regions within the HPV-16 E6 and protein (E6 1–25, E6 16–40, E6 31–55, E6 46–70, E6 61–85, E6 76–100, E6 91–115, E6 106–130, E6 121–145, and E6 136–158). The assay will be performed in triplicate if sufficient cells are available. An HPV-specific T-lymphocyte response will be considered positive if spot-forming units in antigen-containing wells are at least two times higher than corresponding negative-control wells (i.e., a positivity index \geq 2.0). In order to compare each region before vaccination and after injections (after 4 vaccinations, after 7 vaccinations or at the end of the study), a t test for paired samples will be performed, as described previously [36, 37] for regions with increasing positivity index after vaccinations.

CYTOKINE/CHEMOKINE ANALYSIS

Plasma samples collected from blood specimens drawn at Visits 1, 5, 8, and 9 may be analyzed at UAMS for cytokine/chemokine panel which may include of IL-1 β , IL-1 receptor agonist (IL-1RA), IL-2, IL-4, IL-5, IL-6, IL-7, IL-8, IL-9, IL-10, IL-12 (p70), IL-13, IL-15, IL-17A, eotaxin, basic fibroblast growth factor (FGF), G-CSF, GM-CSF, IFN γ , IFN γ induced protein 10 (IP-10), monocyte chemotactic protein 1 (MCP-1), MIP-1 α , MIP-1 α , platelet-derived growth factor subunit B (PDGF-BB), regulated on activation, normal T-cell expressed and secreted (RANTES), TNF- α , vascular endothelial growth factor (VEGF), IL-2 receptor α (IL-2R α), chemokine (C-X-C motif) ligand 1 (CXCL1), hepatocyte growth factor (HGF), IFN- α -2, LIF, chemokine (C-C motif) ligand 7 (CCL7), macrophage migration inhibitory factor (MIF), chemokine (C-X-C motif) ligand 9 (CXCL9), β nerve growth factor (β NGF), stem cell factor (SCF), stem cell growth factor β (SCGF- β), TRAIL, IL-16, and IL-18.

DNA SEQUENCING OF ORAL WASH AND STOOL SAMPLES

Extraction of microbial DNA will be performed at UAMS using the MoBio PowerFecal DNA Isolation Kit (QIAGEN, Cat. No. 12830-50, California) or ZymoBioMICS DNA Miniprep Kit (Zymo Research Cat. No. D4300, Irvine, California). Quality of isolated DNA samples may be determined by agarose gel image and OD 260/280 ratio (OD 260/280 = 1.8^{2} .0). Microbiome diversity analysis may be performed in two methods - Illumina MiSeq/HiSeq and MiniON Flow Cell. For research purposes only, the UAMS bioinformatics researchers will evaluate the quality of data acquisition between two methods of DNA sequencing and provide the microbiome profiling data of DNAs in the fecal samples from subjects with head and neck cancer.

